9.7. Genetics

A blood sample will be collected for pharmacogenetic analysis as specified in the Schedule of Activities (Section 2), where local regulations allow.

Samples will not be used to conduct unspecified disease or population genetic research either now or in the future. Samples will be used to investigate variable exposure or response to LY3154885 and to investigate genetic variants thought to play a role in neurodegenerative diseases or neurological disorders. Assessment of variable response may include evaluation of AEs or differences in efficacy.

All samples will be coded with the subject number. These samples and any data generated can be linked back to the subject only by the investigative site personnel.

Samples will be retained for a maximum of 15 years after the last subject visit, or for a shorter period if local regulations and/or ERBs/IRBs impose shorter time limits, for the study at a facility selected by Lilly. This retention period enables use of new technologies, response to regulatory questions, and investigation of variable response that may not be observed until later in the development of LY3154885 or after LY3154885 is commercially available.

Molecular technologies are expected to improve during the 15-year storage period and therefore cannot be specifically named. Regardless of technology utilized, data generated will be used only for the specific research scope described in this section.

9.8. Biomarkers

Biomarker research is performed to address questions of relevance to drug disposition, target engagement, pharmacodynamics, mechanism of action, variability of patient response (including safety), and clinical outcome. Sample collection is incorporated into clinical studies to enable examination of these questions through measurement of biomolecules including DNA, RNA, proteins, lipids, and other cellular elements.

Blood samples for non-pharmacogenetic biomarker research will be collected at the times specified in the Schedule of Activities (Section 2) where local regulations allow.

Samples will be used for research on the drug target, disease process, variable response to LY3154885, mechanism of action of LY3154885, and/or research method, or for validating diagnostic tools or assay(s).

All samples will be coded with the subject number. These samples and any data generated can be linked back to the subject only by the investigative site personnel.

Samples will be retained for a maximum of 15 years after the last subject visit, or for a shorter period if local regulations and/or ERBs/IRBs impose shorter time limits, at a facility selected by Lilly. This retention period enables use of new technologies, response to regulatory questions, and investigation of variable response that may not be observed until later in the development of LY3154885 or after LY3154885 is commercially available.

9.9. Health Economics

This section is not applicable for this study.

10. Statistical Considerations and Data Analysis

10.1. Sample Size Determination

The sample size is customary for Phase 1 studies evaluating safety and PK, and is not powered on the basis of statistical hypothesis testing.

Subjects who are randomized but not administered treatment or do not complete all treatment periods/doses may be replaced to ensure that enough subjects complete all parts of the study. Replacement subjects will be allocated the same treatment/sequence as the dropout subjects. In Part A, a replacement subject's treatment assignment will follow that of the subject being replaced but may not require completion of all study periods.

10.2. Populations for Analyses

10.2.1. Study Participant Disposition

A detailed description of subject disposition will be provided at the end of the study.

10.2.2. Study Participant Characteristics

The subject's age, sex, weight, BMI, height, race, or other demographic characteristics will be recorded and may be used in the PK and safety analyses as quantitative or classification variables. These data will be summarized using standard descriptive statistics.

10.3. Statistical Analyses

Statistical analysis of this study will be the responsibility of Lilly or its designee.

Pharmacokinetic analyses will be conducted on data from all subjects who receive at least 1 dose of the investigational product and have evaluable PK data.

Safety analyses will be conducted for all enrolled subjects, whether or not they completed all protocol requirements.

Additional exploratory analyses of the data will be conducted as deemed appropriate. Study results may be pooled with the results of other studies for population PK analysis purposes to avoid issues with post hoc analyses and incomplete disclosures of analyses.

10.3.1. Safety Analyses

10.3.1.1. Clinical Evaluation of Safety

All investigational product and protocol procedure AEs will be listed, and if the frequency of events allows, safety data will be summarized using descriptive methodology.

The incidence of symptoms for each treatment will be presented by severity and by association with investigational product as perceived by the investigator. Symptoms reported to occur prior to study enrollment will be distinguished from those reported as new or increased in severity during the study. Each symptom will be classified by the most suitable term from the medical regulatory dictionary.

The number of investigational product-related SAEs will be reported.

10.3.1.2. Statistical Evaluation of Safety

Safety parameters that will be assessed include AEs, clinical laboratory parameters, vital signs, and ECG parameters. The parameters will be listed and summarized using standard descriptive statistics. Additional analysis will be performed if warranted upon review of the data. All planned safety analyses will be detailed in the statistical analysis plan (SAP).

10.3.2. Pharmacokinetic Analyses

10.3.2.1. Pharmacokinetic Parameter Estimation

Pharmacokinetic parameter estimates for LY3154885 will be calculated by standard noncompartmental analysis methods. Parameters for analysis will be maximum observed drug concentration (C_{max}), time to C_{max} (t_{max}), and area under the concentration versus time curve (AUC) of LY3154885 following single and multiple doses of LY3154885. Following multiple dosing, accumulation ratios based on LY3154885 AUC will be calculated as follows: AUC Day 14 / AUC Day 1 and AUC Day 7 / AUC Day 1. Other PK parameters such as half-life, apparent clearance, and apparent volume of distribution may be reported using noncompartmental analysis methods.

If appropriate data are obtained, renal clearance of LY3154885 will be calculated as the ratio of amount excreted/AUC. This will be compared to the unbound glomerular filtration rate, which is estimated using creatinine clearance.

If available, plasma concentration data for itraconazole and its metabolites (if applicable) will be summarized or listed in the clinical study report, and the data may subsequently be used for exploratory model development. A noncompartmental PK analysis of itraconazole and its metabolites may be conducted if deemed valuable to the interpretation of the study results but is not required to complete the clinical study report.

10.3.2.2. Pharmacokinetic Statistical Inference

Descriptive statistics of the PK parameters calculated from Parts A, B, C, and D will be presented by treatment. The following details are noted for the respective sections.

Part A: The PK parameters C_{max} and AUC for LY3154885 will be evaluated to estimate the dose-exposure proportionality of LY3154885 using a linear-mixed-effect power model. In this model, log-transformed dose will be the independent variable and subject will be a random effect. Both C_{max} and AUC will be log-transformed prior to analysis. The least-squares (LS) means for each treatment together with the treatment differences and associated 90% confidence intervals (CIs) will be estimated from the model. These estimates will be back-transformed to present geometric means, the ratios of geometric means, and the corresponding 90% CIs.

Part B: The PK parameters C_{max} and AUC for LY3154885 when administered alone and with itraconazole will be compared using an analysis of variance (ANOVA) model. The parameters will be log-transformed prior to analysis. The model will include a fixed-effect for the treatment (LY + itraconazole : LY) and a random effect for subject. The LS means for each treatment, the

difference between the treatment LS means (LY3154885 + itraconazole – LY3154885), and the associated 90% CIs will be estimated from the ANOVA model and back-transformed from the log scale to provide estimates of the geometric means, geometric mean ratio, and corresponding 90% CIs. The t_{max} of LY3154885 for both treatments will be analyzed using a Wilcoxon signed-rank test. An estimate of the median difference and 90% CI will be calculated.

Part C: The plasma PK parameters C_{max} and AUC for LY3154885 obtained on Day 14 will be evaluated to estimate the dose-exposure proportionality of LY3154885 using a linear-mixed-effect power model. For details of the model, see Part A above.

Plasma concentrations of LY3154885 will be evaluated graphically and/or descriptively to assess the achievement of steady-state, but no formal analysis will be performed for attainment of steady-state.

Part D:

Effect of formulation: The AUC and C_{max} for LY3154885 following administration with a capsule and tablet formulation in a fasted state will be log transformed and analyzed using a mixed effects ANOVA model. The model will include fixed effects for formulation (capsule : tablet). The LS means for each formulation and the 90% CI for the difference in means will be estimated from the ANOVA model and back-transformed from the log scale to provide estimates of the geometric means and 90% CIs for the ratio of the means. The t_{max} of LY3154885 between formulations will be analyzed using a Wilcoxon signed-rank test. An estimate of the median difference and 90% CI will be calculated.

Effect of high-fat diet: The AUC and C_{max} for LY3154885 following administration with a tablet formulation in the fed state and fasted state will be log transformed and analyzed using a mixed-effects ANOVA model. The model will include fixed effects for food (fed : fasted). The LS means for fed and fasted and the 90% CI for the difference in means will be estimated from the ANOVA model and back-transformed from the log scale to provide estimates of the geometric means and 90% CIs for the ratio of the means. The t_{max} of LY3154885 between fed and fasted will be analyzed using a Wilcoxon signed-rank test. An estimate of the median difference and 90% CI will be calculated.

10.3.3. Exploratory Pharmacodynamic Analyses

Endpoints from the DSST and HVLT will be summarized by domain (as appropriate), time, and treatment. Change from baseline may be displayed as appropriate.

Further details of analyses will be provided in the SAP.

10.3.4. Exploratory Pharmacokinetic/Pharmacodynamic Analyses

No LY3154885 exposure-response analyses are planned; however, analyses may be conducted for exploratory purposes based on review of the data.

10.3.5. Data Review During the Study

Access to safety and tolerability data is scheduled to occur after every dosing session (see Sections 5.1.1, 5.1.2, 5.1.3, and 5.1.4 [study design], and 5.5 [dose justification] for further details). Pharmacokinetic data will be reviewed to guide implementation of this study (such as adjustment to blood sampling time) and to support dose escalations at the following decision points:

- In Part A, LY3154885 PK data (up to 48 hours postdose) from Doses 1 to 3 will be reviewed prior to administration of Dose 5
- In Part A, LY3154885 PK data (up to 48 hours postdose) from Dose 5 will be reviewed prior to administration of Dose 6
- In Part B, LY3154885 PK data (up to 96 hours postdose) will be reviewed to inform a decision on the conduct of Part C and D
- In Part C, LY3154885 PK data (up to 24 hours postdose on Day 15) from the low dose (Cohort 4) will be reviewed prior to administration of the high dose (Cohort 6)

The investigator and the Lilly sponsor team will make the determination regarding dose escalation based upon their review of the safety and tolerability data and any available PK data. Data reviews may be added as deemed appropriate by the sponsor without a protocol amendment.

Appendix 1. Abbreviations and Definitions

Term	Definition
ABPM	ambulatory blood pressure monitoring
AE	adverse event: Any untoward medical occurrence in a patient or clinical investigation subject administered a pharmaceutical product that does not necessarily have a causal relationship with this treatment. An AE can therefore be any unfavorable and unintended sign (including an abnormal laboratory finding), symptom, or disease temporally associated with the use of a medicinal (investigational) product, whether or not related to the medicinal (investigational) product.
ALP	alkaline phosphatase
ALT	alanine aminotransferase
ANOVA	analysis of variance
AST	aspartate aminotransferase
AUC	area under the concentration versus time curve
blinding	A procedure in which one or more parties to the study are kept unaware of the treatment assignment(s). Unless otherwise specified, blinding will remain in effect until final database lock. A single-blind study is one in which the investigator and/or his/her staff are aware of the treatment but the subject is not, or vice versa, or when the sponsor is aware of the treatment but the investigator and/or his/her staff and the subject are not. A double-blind study is one in which neither the subject nor any of the investigator or sponsor staff who are involved in the treatment or clinical evaluation of the subjects are aware of the treatment received.
BMI	body mass index
BP	blood pressure
CI	confidence interval
CIOMS	Council for International Organizations of Medical Sciences
C_{max}	maximum observed drug concentration
CNS	central nervous system
complaint	A complaint is any written, electronic, or oral communication that alleges deficiencies related to the identity, quality, purity, durability, reliability, safety or effectiveness, or performance of a drug or drug delivery system.
compliance	Adherence to all the study-related requirements, good clinical practice (GCP) requirements, and the applicable regulatory requirements.
confirmation	A process used to confirm that laboratory test results meet the quality requirements defined by the laboratory generating the data and that Lilly is confident that results are accurate. Confirmation will either occur immediately after initial testing or will require that samples be held to be retested at some defined time point, depending on the steps required to obtain confirmed results.

CP	clinical pharmacologist
CRF	case report form
CRP	clinical research physician: Individual responsible for the medical conduct of the study. Responsibilities of the CRP may be performed by a physician, clinical research scientist, global safety physician, or other medical officer.
CRU	clinical research unit
C-SSRS	Columbia-Suicide Severity Rating Scale
CV	cardiovascular
CYP	cytochrome P450
D1 PAM	positive allosteric modulator (also called “potentiator”) of the dopamine D1 receptor
DSST	Digital Symbol Substitution Test
ECG	electrocardiogram
enroll	The act of assigning a subject to a treatment. Subjects who are enrolled in the study are those who have been assigned to a treatment.
enter	Subjects entered into a study are those who sign the informed consent form directly or through their legally acceptable representatives.
ERB	ethical review board
GCP	good clinical practice
GLP	good laboratory practice
hERG	human ether-a-go-go-related gene
HIV	human immunodeficiency virus
HR	heart rate
HVLT	Hopkins Verbal Learning Test
IB	Investigator’s Brochure
IC₅₀	half-maximal inhibitory concentration
ICF	informed consent form
ICH	International Council for Harmonisation
informed consent	A process by which a subject voluntarily confirms his or her willingness to participate in a particular study after having been informed of all aspects of the study that are relevant to the subject’s decision to participate. Informed consent is documented by means of a written, signed, and dated informed consent form.

Investigational medicinal product (IMP)	A pharmaceutical form of an active ingredient or placebo being tested or used as a reference in a clinical study, including products already on the market when used or assembled (formulated or packaged) in a way different from the authorized form, or marketed products used for an unauthorized indication, or marketed products used to gain further information about the authorized form.
investigator	A person responsible for the conduct of the clinical study at a study site. If a study is conducted by a team of individuals at a study site, the investigator is the responsible leader of the team and may be called the principal investigator.
IRB	institutional review board
LC/MS/MS	liquid chromatography with tandem mass spectrometry
LS	least squares
MAD	multiple-ascending dose
MTD	maximum tolerated dose
NOAEL	no-observed-adverse-effect level
NOEL	no-observed-effect level
open-label	A study in which there are no restrictions on knowledge of treatment allocation; therefore, the investigator and the study participant are aware of the drug therapy received during the study.
PD	Parkinson's disease
PI	principal investigator
PK	pharmacokinetic(s)
POMS-2	Profile of Mood States Second Edition
PR	pulse rate
PWC-20	Penn Physician Withdrawal Checklist
QTc	QT interval corrected for heart rate
QTcf	QT interval corrected for heart rate using Fridericia's formula
randomize	the process of assigning subjects/patients to an experimental group on a random basis
SAD	single-ascending dose
SAE	serious adverse event
SAP	statistical analysis plan
screen	The act of determining if an individual meets minimum requirements to become part of a pool of potential candidates for participation in a clinical study.

SRP	safety review panel
SUSAR	suspected unexpected serious adverse reaction
TBL	total bilirubin level
TEAE	treatment-emergent adverse event: Any untoward medical occurrence that emerges during a defined treatment period, having been absent pretreatment, or worsens relative to the pretreatment state, and does not necessarily have to have a causal relationship with this treatment
t_{max}	time to C _{max}
UGT	UDP-glucuronosyltransferase
ULN	upper limit of normal

Appendix 2. Clinical Laboratory Tests

Clinical Laboratory Tests

Hematology^a:

Hematocrit
 Hemoglobin
 Erythrocyte count (RBC)
 Mean cell volume
 Mean cell hemoglobin
 Mean cell hemoglobin concentration
 Leukocytes (WBC)
 Platelets
 Absolute counts of:
 Neutrophils
 Lymphocytes
 Monocytes
 Eosinophils
 Basophils

Urinalysis^b:

Specific gravity
 pH
 Protein
 Glucose
 Ketones
 Bilirubin
 Urobilinogen
 Blood
 Nitrite
 Leukocytes
 Microscopic examination of sediment (if dipstick abnormal)^b

Clinical Chemistry:

Sodium
 Potassium
 Bicarbonate
 Chloride
 Calcium
 Glucose (random)
 Total cholesterol
 Total protein
 Albumin
 Total bilirubin
 Alkaline phosphatase (ALP)
 Aspartate aminotransferase (AST)
 Alanine aminotransferase (ALT)
 Creatinine
 Gamma-glutamyl transferase (GGT)^a
 Urea

Hepatitis B surface antigen^{a,c}

Hepatitis C antibody

HIV^{a,c}

Pregnancy test (if applicable)^d

FSH (if applicable)^{a,e}

Thyroid stimulating hormone (TSH)^a

Note: Results of these assays will be validated by the local laboratory at the time of testing. Additional tests may be performed or autocalculated by the laboratory as part of its standard panel that cannot be removed. Some of the above parameters are calculated from measured values. Inclusion or omission of calculated values will not be considered a protocol deviation.

Abbreviations: FSH = follicle-stimulating hormone; HIV = human immunodeficiency virus; RBC = red blood cells; WBC = white blood cells.

a Performed at screening only.

b If clinically indicated, per investigator's discretion.

c Tests may be waived if they have been performed within 6 months before screening with reports available for review.

d Serum test at screening and admission; urine test at all other times. Women with confirmed nonchildbearing potential status can be exempted from further pregnancy tests during the study after screening.

e To be performed only at screening for assessment of menopause status, if necessary.

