9.4. Safety

9.4.1. Laboratory Tests

For each subject, laboratory tests detailed in [Appendix 2](#) should be conducted according to the Schedule of Activities (Section 2).

With the exception of safety laboratory test results that may unblind the study, Lilly or its designee will provide the investigator with the results of laboratory tests analyzed by a central vendor, if a central vendor is used for the study.

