9.5.3 Clinical laboratory parameters

All clinical chemistry and hematology data will be summarized by part, parameter and treatment, and listed. Where postdose data is available, changes from baseline, where baseline is defined as Day 1 predose will also be presented. Urinalysis data will be listed. Additionally, clinical chemistry, hematology and urinalysis data outside the reference ranges will be listed and flagged on individual subject data listings.

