13.3 Insufficient Data for Presentation

Some of the TFLs may not have sufficient numbers of subjects or data for presentation. If this occurs, the blank TFL shell will be presented with a message printed in the centre of the table, such as, "No serious adverse events occurred for this study."

Leo Document ID = 563c5820-336a-45c5-b10a-5be1c73cad89

Approver: PPD

Approval Date & Time: 16-Jul-2019 10:35:33 GMT

Signature meaning: Approved

Approver: PPD

Approval Date & Time: 17-Jul-2019 19:42:59 GMT

Signature meaning: Approved

Approver: PPD

Approval Date & Time: 18-Jul-2019 12:49:53 GMT

Signature meaning: Approved

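### Appendix 2 marks the whole hematology panel as screening only, while SAP 9.5.3 summarises hematology by treatment with change from Day 1 predose

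*Protocol*

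**What the plan says.** **Collection.** Protocol 9.4.1 states that "For each subject, laboratory tests detailed in" Appendix 2 are to follow the Schedule of Activities in Section 2. Section 2 has one undivided row for clinical laboratory tests in each part and refers to Appendix 2 for its content. In Appendix 2, marker a stands on the Hematology heading and so covers every analyte beneath it. The footnote is "a Performed at screening only". The Clinical Chemistry heading has no marker.

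**Analysis.** SAP 9.5.3 states: "All clinical chemistry and hematology data will be summarized by part, parameter and treatment, and listed". It continues: "Where postdose data is available, changes from baseline, where baseline is defined as Day 1 predose will also be presented". Urinalysis, by contrast, is only listed. SAP Section 11 declares no changes from the protocol's analyses.

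**Use during the study.** Laboratory results are among the safety data to be assessed before dose escalation in Part A (Protocol 5.1.1) and between cohorts in Part C (Protocol 5.1.3).

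**The concern.** A panel taken only at screening has no Day 1 predose value and no value under treatment, yet the SAP plans a by-treatment summary and a change score for it. Either the collection instruction or the analysis text is wrong.

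This is a first-in-human study. A site that follows Appendix 2 as printed would run no scheduled hematology after screening. The final report would then have no scheduled hematology with which to compare LY3154885 and placebo in Parts A to C, and the laboratory data reviewed before escalation would lack it too. The gap could not be repaired at the analysis stage, because the values would never have been obtained.

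**Working it through.** **1. Reproduce the draw counts.** The inputs are the laboratory rows of Section 2 for a subject who completes, leaving out screening and early discontinuation, and the clinical laboratory rows of Appendix 5.

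| Part | Occasions in Section 2, without Day -2 | Sum | Appendix 5 | With Day -2 | Of these, scheduled hematology if marker a is followed |
|---|---|---|---|---|---|
| A | Day 1 predose × 3, Day 3 × 3, follow-up | 3 + 3 + 1 = 7 | 7 | 7 + 1 = 8 | 0 |
| B | Days 1, 8, 14, 18, follow-up | 4 + 1 = 5 | 5 | 5 + 1 = 6 | 0 |
| C | Days 1, 7, 15, follow-up | 3 + 1 = 4 | 4 | 4 + 1 = 5 | 0 |
| D | 5 per period × 3, follow-up | 15 + 1 = 16 | 16 | 16 (no Day -2 draw) | 0 |

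The sums agree with Appendix 5 once the Day -2 draw is set aside. In each part, one of the 7 / 5 / 4 / 16 draws is the predose draw before the first dose; the other 6 / 4 / 3 / 15 follow that dose.

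**2. Look for another source of scheduled hematology.** There is none. The remaining routes are not scheduled:
- Appendix 4 has a hematology panel, but it is triggered by a hepatic abnormality.
- Appendix 5 allows additional samples if they are needed for safety.
- The Appendix 2 note says: "Additional tests may be performed or autocalculated by the laboratory as part of its standard panel that cannot be removed". That depends on the laboratory and may yield nothing.

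**3. Set the SAP against what would be collected.** The SAP's baseline is Day 1 predose. Under marker a that draw carries no hematology, so even a stray postdose result would have no scheduled baseline to be compared with.

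**4. Check whether a version gap explains it.** SAP Section 3 says that the SAP was written against the original protocol and amendment (a). The current protocol is amendment (b), whose summary of changes lists no change to Appendix 2. The mismatch therefore does not appear to come from the amendment.

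**The case against.** The strongest reply is that the point hangs on one superscript in a multi-column table, and that the SAP text adapts to whatever is collected.

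**Position of the marker.** This part stands as a caution. The lettering shows other irregularities: hepatitis C antibody has no marker although hepatitis B and HIV do, and FSH carries two letters that both mean screening only. Marker a may be a sponsor's slip or a fault of text extraction. Against general garbling, the same letter sits plausibly on hepatitis B, HIV, FSH and TSH. A slip in the approved document would still be an instruction that the site could follow.

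**Conditional SAP wording.** Changes from baseline are promised only where postdose data exist, and SAP 13.3 allows for outputs that cannot be filled: "Some of the TFLs may not have sufficient numbers of subjects or data for presentation". This softens the conflict but does not remove it. The by-treatment summary has no such condition. In Part A each subject is to receive both LY3154885 and placebo, so a screening value belongs to no treatment. In Parts B and C, screening values tabulated by arm would say nothing about treatment. SAP 13.3 governs how an empty output is shown; it does not supply data.

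**Unscheduled results.** Safety samples and for-cause panels remain possible. They mitigate the gap, but they would come from selected subjects at irregular times.

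A reader might infer three stronger points that the documents do not support:
- *That GGT shows the same contradiction*, since Appendix 2 prints "Gamma-glutamyl transferase (GGT)^a". A single analyte kept for screening fits the SAP's conditional sentence, and GGT for cause is covered by Protocol 9.4.8.1 and Appendix 4.
- *That eosinophilia in the liver criteria of Protocol 8.1 proves that routine hematology was intended.* The same list uses INR, which is absent from Appendix 2 and appears only in the event-triggered panel of Appendix 4.
- *That the primary objective fails.* The primary endpoint is TEAE incidence, which remains analysable.

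**Conclusion.** The conflict holds for the hematology panel and should be fixed. As written, scheduled hematology after screening is zero on every one of the 7 / 5 / 4 / 16 draws per completer in Parts A / B / C / D, and on the Day -2 draws in Parts A to C. The SAP analysis would have neither a scheduled baseline nor scheduled values under treatment, and the escalation reviews in Parts A and C would have no scheduled hematology. Routine chemistry and the primary endpoint are unaffected.

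The conclusion assumes that marker a stands on the Hematology heading in the approved PDF and that the site applies the footnote literally. Confidence is medium for that reason. The documents do not show which of the two texts the sponsor intended. The SAP's treatment of hematology, summarised where urinalysis is only listed, is consistent with an expectation of routine collection but does not settle it.

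**What to change.** First check the marker against the approved PDF. If it is there, reconcile Appendix 2 with SAP 9.5.3 in one of two ways:

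- **If the SAP analysis is intended:** remove marker a from the Hematology heading, so that the panel runs on the laboratory draws already in Section 2. This needs no new visits and a small assay cost on 7 / 5 / 4 / 16 draws per completer, or 8 / 6 / 5 / 16 if Day -2 is included. Appendix 5 allots 8 mL per draw without saying whether this covers a hematology tube; the laboratory should confirm.
- **If screening-only collection is intended:** amend SAP 9.5.3 so that hematology is listed and not summarised, and state that no scheduled on-treatment hematology comparison will be made. This costs one SAP paragraph.

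No change to GGT is needed to resolve this point.
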